4.7 All-Cause Mortality

All-cause mortality is measured by the proportion of participants with a successful outcome (life) or unsuccessful outcome (death) by Day 28.

Let π_A and π_S represent the all-cause mortality rate of this outcome for Ampion and control during the study. Then it is desired to demonstrate that the mortality rate for Ampion is different than the corresponding rate for the control. Formally, this is presented as:

$H_0: \pi_A = \pi_S$ versus $H_A: \pi_A \neq \pi_S$

This will be tested utilizing the appropriate chi-square test or Fisher's exact test utilizing PROC FREQ with the EXACT option, if necessary. Also, the median time to death will be tested for difference between the two groups via the log-rank test. The test will be performed using PROC LIFETEST. The time to event distributions in each group will be estimated using the method of Kaplan and Meier.

4.8 Cytokine Profile

The exploratory endpoint, cytokine profile, is measured as the modulation of cytokine levels from baseline to Day 5.

The hypotheses to be tested are:

$H_0: \mu_A = \mu_S$ versus $H_A: \mu_A \neq \mu_S$

Where μ_A and μ_S represent the mean percent change from baseline in the cytokine levels at day 5 for Ampion and Placebo after randomization. The difference between Ampion and Placebo with respect to the percent change from baseline at day 5 will be tested utilizing a two-sample t-test via PROC TTEST. To assess any potential time trends, an exploratory repeated measures analysis of variance will be performed with terms for treatment, time, and the interaction of the two. This will be done utilizing PROC GLM with the REPEATED option. Also, the rates of the various adverse events and serious adverse events will be presented in tables, but otherwise not analyzed statistically.

5. DEFINITIONS

5.1 Adverse Event:

An adverse event (AE) is defined as any undesired medical occurrence in a patient or clinical investigation patient receiving a pharmaceutical product and which does not necessarily have a causal relationship with this treatment. An AE can therefore be any unfavorable sign and unintended sign (including an abnormal laboratory finding), symptom, or disease temporarily associated with the use of a study drug, whether or not related to the study drug.

AEs will be graded for severity using the following categories. Missing grade will be assigned a grade of 3 (severe) in tabulations.

- **Grade 1 (MILD):** The symptom is barely noticeable to the study patient and does not influence performance or functioning. Concomitant medication is not ordinarily indicated for relief of mild AEs.
- **Grade 2 (MODERATE):** The symptom is of sufficient severity to make the study patient uncomfortable and to influence performance of daily activities. Concomitant medication

may be indicated for relief of moderate AEs.

- **Grade 3 (SEVERE):** The symptom causes severe discomfort, sometimes of such severity that the study patient cannot continue in the study. Daily activities are significantly impaired or prevented by the symptom. Concomitant medication may be indicated for relief of severe AEs.

Relationship to study drug will be coded using the following categories. Missing relatedness will be assigned to related in tabulations.

- **Unrelated:** The adverse event is unlikely to have been caused by study drug.
- **Possibly related:** It is unclear whether the adverse event may have been caused by study drug.
- **Related:** The adverse event is likely to have been caused by study drug.

5.2 Serious Adverse Event:

A serious adverse event (SAE) is defined as an adverse event that

- Results in death
- Is life-threatening (patient is at immediate risk of death from the event as it occurred)
- Requires prolongation of existing hospitalization
- Results in persistent or significant disability/incapacity
- Results in a congenital anomaly/birth defect

5.3 Treatment-Emergent AE:

A treatment-emergent AE (TEAE) is any AE that begins or increases in severity after the initial dose of study drug.

5.4 Age:

Subject's age is defined as its integer value in years at enrollment.

5.5 Baseline:

For any variable, unless otherwise defined, baseline is the last assessment taken prior to the first study drug administration.

5.6 Change from Baseline:

6. ANALYSIS SUBSETS

6.1 Data Subsets

6.1.1 Safety Analysis Set

The safety analysis population is defined as all patients who are randomized and receive study treatment (Ampion or SOC). Patients will be analyzed as treated. Summaries of data will include all data assigned to a nominal visit whether within the visit window.

6.1.2 Intent to Treat (ITT) Analysis Set

The intent-to-treat (ITT) analysis population is defined as all randomized patients. All efficacy analyses will be performed in the ITT population. Patients will be analyzed as randomized.

7. INTERIM ANALYSIS AND EARLY STOPPING GUIDELINES

7.1 Interim Analysis

The interim analysis is planned near the end of enrollment, after 150 patients, to test the protocol assumptions and estimates for clinical improvement, all-cause mortality rates and secondary endpoints as the available information and nature of the COVID-19 pandemic is rapidly evolving, which may impact estimates for both Ampion and control. The interim analysis will be used to determine if the sample size should remain at the planned 200 patients or increase based on the results of this analysis.

The interim analysis will be conducted on the primary and secondary endpoint data at an alpha level of 0.001, and thus the overall alpha level for the final test will be performed at $\alpha=0.047$ instead of the nominal value of $\alpha=0.05$. The sponsor also reserves the right to alter the final sample size if the assumptions of clinical improvement are not satisfied at this interim analysis.

The interim analysis uses the same hypothesis test described in the final analysis where μ_A and μ_S represent the mean changes in the ordinal scale for Ampion and control respectively. Then, it is desired to demonstrate that the mean change for Ampion is different than the corresponding mean change for the control, respectively. Formally, this is presented as:

$H_0: \mu_A = \mu_S$ versus $H_A: \mu_A \neq \mu_S$

The difference between Ampion and Placebo with respect to the change from baseline at Day 5 and Day 28 will be tested utilizing a Wilcoxon rank-sum test. To assess any potential time trends, an exploratory repeated measures analysis of variance will be performed with terms for treatment, time, and the interaction between the two.

7.2 Blinding Controls at Interim Analysis

The interim analysis will involve unblinded data. Only a small, sequestered team will have access to the unblinded data and results. The data will not be transferred, or results viewed by any person involved in the day-to-day conduct of the clinical trial, including, but not limited to the blinded sponsor staff, Medical Monitor, and/or blinded CRO staff. These individuals will remain blinded to the results.

The unblinded team will be responsible for obtaining the required material for the analysis from the study's unblinded data manager (DM) for the clinical trial. The unblinded team will present the results of the interim analysis to the sponsor in a blinded fashion (e.g., a simple recommendation to increase sample size or keep sample size as defined in the SAP without presenting details surrounding the raw data, results, or efficacy conclusions).

All individuals on the sequestered team who are unblinded will be documented and archived by the sponsor.

7.3 Stopping Rules

The study may be stopped upon recommendation by the safety monitoring committee.

8. DATA HANDLING AND ELECTRONIC TRANSFER OF DATA

See Data Management Plan (DMP).

8.1 Handling of Missing and Incomplete Data

All data collected under this study protocol will be included in the assessment of patient safety. Missing or incomplete AE data will assume greatest relationship to study drug and/or severity.

Incomplete adverse event and concomitant medication dates will be imputed as described in Section 11. If imputed dates are used, then they will be identified as such in the final study report. If an AE start date is missing or partially missing and no additional information is available in order to establish whether the event started before or after the dose of study drug, the event will be considered to have started after dose. Partially missing dates where the month and year is prior to Day 0 will not be classified as post dose.

For the ordinal score effectiveness endpoint analysis of clinical outcomes at Day 5 and Day 28 a sensitivity analysis will be performed for all patients that have been discharged from the hospital, cannot be reached via telephone contact, and their death status is not known. The sensitivity analysis will be performed where missing ordinal scale status at Day 5 and Day 28 will be replaced as having died (Ordinal score 8).

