**Study Design:**

Overall Design

This is a Phase II randomized, double-blinded, placebo-controlled study in adult participants with respiratory distress due to COVID-19.

Screening

Interested participants will sign the appropriate informed consent document(s) prior to completion of any study procedures. The investigator will review symptoms, risk factors and other non-invasive inclusion, including COVID testing, and exclusion criteria prior to any study procedures. If the participant is eligible after this review, then the site will perform the necessary, if any, study procedures to confirm eligibility.

Double-Blind Treatment and Assessment

Participants will be randomized 1:1 to active or placebo using a random allocation sequence stratified by COVID-19 disease severity (severe or critical). Given the changing nature of the pandemic, periodic adjustments to the allocation ratio may be made in an effort to achieve equal allocation across the treatment arms at the end of the enrollment. There are two planned treatment arms:

Treatment Arm	Study Intervention
Active	Ampion for 5-days
Control	Placebo for 5-days

The general sequence of events during the treatment and assessment period:

- Complete baseline procedures and sample collection.
- Participants are randomized to Ampion or placebo.
- Participants receive study intervention (active or placebo) inhaled via nebulization for 5 days.
- Complete safety monitoring, study procedures, and sample collection.

The Schedule of Assessments is shown in [Section 1.2](#). Visit types are described as follows:

Study Day	Visit Description	Visit Type
1	Baseline measures prior to treatment	Site
1-5	Treatment	Site
28, 60	Follow-up	Telephone

Post-Treatment Follow-up

Post-treatment follow-up will occur after Day 5 to assess mortality, clinical status and adverse events.

Sponsor: Ampio Pharmaceuticals, Inc.	Investigational Product: Ampion™

Disclosure Statement
 
The treatment in this study will be blinded to the investigator(s) and subject(s).
	

Data Safety Monitoring Board
 
There will be a Data Safety Monitoring Board (DSMB). Safety, including incidence of AEs/SAEs will be evaluated by a DSMB throughout the study.
	

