## 1.2 Schedule of Assessments (SoA)

Visits will be conducted as described:

	Screen	Treatment					Hospitalization	Follow-up	
		1 	2	3	4	5		28	60
Study Day	-3 to Baseline						Every day until discharge		
Visit Window (± days)	--	--	--	--	--	--	--	3	3
COVID-19 diagnosis	X								
Informed consent	X								
Medical history and pre-existing conditions	X								
Inclusion/exclusion criteria	X	X							
Urine pregnancy test		X							
Demographics		X							
Randomization		X							
Treatment (active or placebo)		X	X	X	X	X			
Vital signs		X	X	X	X	X	X		
Blood oxygen saturation		X	X	X	X	X	X		
ECG (telemetry) 		X	X	X	X	X	X 		
Hematology 		X		X		X	X 		
Biochemistry 		X		X		X	X 		
Cytokine/chemokine assay 		X				X	X 		
Mortality							X	X	X
Ordinal scale for clinical status		X	X	X	X	X	X	X	X
NEWS2 score		X	X	X	X	X	X	X	X
Hospital LOS and ICU LOS		X	X	X	X	X	X	X	X
Date of intubation/extubation, days on ventilation			X	X	X	X	X	X	X
Concomitant medications		X	X	X	X	X	X	X	X
Adverse events		X	X	X	X	X	X	X	X

 Day 1 baseline assessments occur before the first dose of treatment; pregnancy test to be conducted as applicable.

 Telemetry or 12 ECG lead monitored once daily.

 Hematology and biochemistry tests are performed at baseline and every other day through hospitalization.

 Cytokine and chemokine assays are collected at baseline before treatment, at Day 5 after treatment, and at discharge.

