The clinical effects, safety, and tolerability of treatment will be evaluated from baseline through Day 60. Evaluations at screening and during the 5-day treatment occur in person. Evaluations after the 5-day treatment to the end of the study (days 7 to 60) will typically occur via telephone contact unless the patient is in an inpatient setting.

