## 5 STUDY PLAN, PROCEDURES, AND ASSESSMENTS

### 5.1 Description of Study Visits

The mortality, clinical effects, safety, and tolerability of treatment will be evaluated from baseline through Day 60. Evaluations at screening and during the 5-day treatment occur in person. Evaluations after the 5-day treatment to the end of the study (days 6 to 60) will typically occur via telephone. The Schedule of Assessments is shown in [Section 1.2](#).

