#### 5.1.3 Treatment Period (Day 1 to Day 5)

The following procedures will be performed during the Treatment Period (Day 1 to Day 5) while subject is hospitalized for the index hospitalization:

- Begin inhalation treatment of study intervention (active or placebo) daily within 6 hours of randomization.
- Concomitant medications/therapies

- Vital signs: heart rate, systolic and diastolic BP, body temperature, respiratory rate
- SpO2 and supplementation oxygen mode/flow rate
- ECG monitoring (telemetry) or 12-lead ECG: record aberrant changes in waves/ intervals.
- Hematology, biochemistry tests – these tests are performed at baseline and every other day through treatment and through hospital.
- Cytokine and chemokine assays – these tests are performed at baseline and at Day 5.
- Ordinal scale and NEWS2 assessments
- Aes

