#### **5.1.5 Post-Treatment Follow-Up (Days 28, 60)**

The following procedures will be performed at all follow-up visits (Days 28, 60):

- Mortality
- Concomitant medications/therapies
- Hospital LOS
- ICU LOS
- Ordinal scale and NEWS2 assessments
- Aes

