### Ordinal Scale for Clinical Improvement

The clinical status will be recorded at every visit from baseline to Day 60 using the World Health Organization (WHO) “Ordinal Scale for Clinical Improvement”. This 8-point ordinal scale was created to be responsive to the eligible patient population, intervention, and course of illness of COVID-19. The score should reflect the highest level of support the subject required on the day being recorded. The following is scores are collected:

Score	Descriptor
0	No clinical or virological evidence of infection
1	No limitation of activities
2	Limitation of activities
3	Hospitalized, no oxygen
4	Hospitalized, oxygen by mask or nasal prongs
5	Hospitalized, non-invasive ventilation or high-flow oxygen
6	Hospitalized, mechanical ventilation
7	Hospitalized, ventilation + additional organ support – pressors, RRT, ECMO
8	Death

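### The documents disagree on whether a participant discharged before Day 5 gets a Day 5 ordinal score, and no primary-analysis rule covers a missing one

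*SAP*

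**What the plan says.** The primary endpoint is change in the WHO ordinal scale to Day 5 and to Day 28, compared by a Wilcoxon rank-sum test (Protocol 9.4.1, SAP 4) in all randomised participants (Protocol 9.2.2, SAP 6.1.2). Discharge before Day 5 is foreseen: Protocol 7.1 ends treatment at discharge if that comes before the end of the five days.

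Some passages leave no contact at which a discharged participant could be scored on Day 5:
- Protocol 5.1.3 lists the ordinal scale among procedures done "while subject is hospitalized for the index hospitalization".
- The synopsis classes Days 1 to 5 as site visits and only Days 28 and 60 as telephone visits, and adds: "Post-treatment follow-up will occur after Day 5 to assess mortality, clinical status and adverse events".
- Protocol 3.1 and SAP 2.3 place evaluations during the treatment days in person.
- Protocol 5.1: "Evaluations after the 5-day treatment to the end of the study (days 6 to 60) will typically occur via telephone". Protocol 3.1: "Evaluations after the 5-day treatment to the end of the study (days 7 to 60) will typically occur via telephone contact"; SAP 2.3 also starts at Day 7.
- Protocol 5.1.5 names only Days 28 and 60 as follow-up visits.

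Other passages expect the score:
- The Schedule of Assessments marks "Ordinal scale for clinical status" on each of Days 1 to 5, with no discharge condition.
- Protocol 5.2: "The clinical status will be recorded at every visit from baseline to Day 60".
- Protocol 9.5 and SAP 8.1 plan a sensitivity analysis in which participants "discharged from the hospital, cannot be reached via telephone contact, and their death status is not known" are given score 8 at Day 5 and Day 28. This takes for granted that discharged participants are telephoned about Day 5.

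**The concern.** A site that follows Protocol 5.1.3 and a site that follows Protocol 5.2 would collect different primary data. Under the first reading, a participant sent home on Day 3 has no Day 5 score, and the plan does not say what the primary test does with that person. PROC NPAR1WAY, the procedure named in SAP 4, cannot rank a missing value, so the likely default is omission. That conflicts with an analysis of all randomised participants.

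The loss would not be random. Early discharge is usually a good outcome, so the missing scores would be concentrated among the best responders. Removing them shrinks any advantage of the arm that discharges sooner, whichever arm that is.

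**Working it through.** **1. Is there a primary-analysis rule?** Four places could hold one.
- SAP 4 and Protocol 9.4.1 name the test and say nothing on missing scores.
- SAP 8.1 and Protocol 9.5 give only a sensitivity analysis. It needs three conditions at once: discharged, unreachable, and vital status unknown. Someone discharged on Day 3, known to be alive and without a Day 5 score falls outside it.
- SAP 9.6 rules out estimation or carry-forward, but only for descriptive analyses.
- SAP 4.2 uses the discharge value when discharge precedes Day 5, but for NEWS2 only.

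So no rule exists for the primary test.

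**2. What would the missing score be?** On the Protocol 5.2 scale, scores 3 to 7 all describe hospitalised patients and 8 is death. A living participant who is still out of hospital on Day 5 is therefore 0, 1 or 2. With a score of 2, change from baseline is 2 − 4 = −2 from baseline 4, and 2 − 5 = −3 from baseline 5. These are among the best changes in the trial, and they are the ones at risk.

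**3. How much could it matter?** The plan gives no figure to reproduce: no Day 5 discharge rate, no missing-score rate, and a power statement that concerns mortality. The size can only be illustrated.

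From the documents: 100 per arm, final two-sided α = 0.047, Wilcoxon test on change from baseline.

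Assumed:
- Baseline 4, 5 or 6 with probability 0.65, 0.30, 0.05.
- Early discharge only from baseline 4 or 5, with relative probability 1 and 0.4.
- Inpatient change of −1, 0, +1, +2 or death with probability 0.27, 0.53, 0.10, 0.05, 0.05 in both arms.
- Discharged participants score 2. Benefit acts only through discharge. A stated share of early discharges is missing at random and omitted.

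Chance that the Day 5 test is significant (thousands of simulated trials per scenario):

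| Early discharge, control / Ampion | None missing | Half missing | All missing |
|---|---|---|---|
| 2% / 5% | 6% | 5% | 4% |
| 5% / 10% | 10% | 7% | 5% |
| 10% / 20% | 24% | 11% | 5% |
| 20% / 40% | 71% | about 38% (36 to 39% across repeat runs) | 5% |
| 20% / 20%, no effect | 4 to 5% | 4 to 5% | 4 to 5% |

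At 10% / 20% the mean difference in change is −0.23 with none missing, −0.14 with half missing and 0.00 with all missing.

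The 5% at full omission follows from the assumption that benefit acts only through discharge. If 15% of Ampion inpatients also improve by one further point, the figures for none, half and all missing are 51, 34 and 16% at 10% / 20%, and 86, 61 and 14% at 20% / 40%.

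The effect is symmetric. If placebo discharges faster (20% against 10%), the chance of detecting the placebo advantage falls from 24% to 11% with half missing and to 2% with all missing.

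**The case against.** The strongest reply is that the plan already intends a Day 5 score after discharge. The Schedule of Assessments and Protocol 5.2 attach no in-hospital condition, the schedule has a separate column for continued hospitalisation, and the sensitivity analysis names Day 5. Protocol 5.1.3 can be read as a list of inpatient procedures rather than an instruction to stop scoring, and telephone use is described only as typical. This shows which reading was probably meant. It does not supply a contact before Day 6, and it leaves the primary test without a rule.

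The contrast with NEWS2 is also weaker than it looks. NEWS2 needs measured vital signs and oxygen saturation, whereas the ordinal status can be taken by telephone. A discharge rule for one measure only is not in itself inconsistent.

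Four stronger readings are tempting and are not supported:
- **The plan scores early discharges as dead.** Score 8 applies only in a sensitivity analysis and only to the narrow three-condition group. In the simulation, with 10% of discharged participants unreachable, significance is 18% at 10% / 20% and 53% at 20% / 40%, with no reversal of direction.
- **The plan expects Ampion patients to leave before Day 5 more often.** Protocol 2.3 reports mean stays of 7 against 11 days, but these are preliminary results from 27 subjects, and means do not fix the share discharged by Day 4. With lognormal stays and coefficients of variation from 0.3 to 1.0, those means give anything from 0% / 9% to 26% / 45% (control / Ampion). This trial also enrols critical patients.
- **False positives rise.** They do not when discharge is equal and there is no effect.
- **Day 28 is compromised too.** Early discharge as such does not affect it, because a Day 28 telephone visit is scheduled.

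**Conclusion.** The concern holds as a conflict in the text plus a missing rule at a primary time point. Both can be checked in the documents without any assumption, and confidence in them is high. If Protocol 5.1.3 is followed and unscored participants are omitted, the Day 5 comparison is biased against the arm with faster discharge. The direction rests only on early discharges being better than average outcomes.

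Confidence in the size is low. With half of early-discharge scores missing, the loss is small at 5% / 10% early discharge and large at 20% / 40%; the documents exclude neither. If sites score every discharged participant on Day 5, the loss disappears, but the text does not ensure that. It should be fixed, because the affected endpoint is primary and the remedy is cheap.

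**What to change.** 1. Reconcile the synopsis visit table, the Schedule of Assessments, Protocol 3.1, 5.1, 5.1.3 and 5.2 (ordinal scale) and SAP 2.3. They should state that Day 5 ordinal status, including any readmission or death, is obtained for every randomised participant, by telephone if already discharged.

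2. In SAP 8.1 and Protocol 9.5, state that the primary Day 5 analysis keeps all ITT participants. One who was discharged alive before Day 5, is not known to be readmitted or dead, and has no recorded score is assigned a pre-specified not-hospitalised category (within 0 to 2), based on the recorded discharge date. Add a sensitivity analysis for possible readmission or death. Settle this before unblinding.

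3. The score-8 analysis may stay as a labelled worst case.

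Cost: wording changes and one short telephone contact. Discharge dates are already collected (Protocol 5.2, Length of Stay), so the fallback needs no new data. Its drawback is that it can mask relapse. At 20% / 40% early discharge, if 10% of Ampion discharges (and no control discharges) are back in hospital at score 4 by Day 5 and every discharge is given score 2, the chance of significance is 71% against 53% with true scores. With 20% readmitted it is 70% against 34%. The fallback should therefore apply only where the telephone contact fails, not replace it.
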